Official Title: Preliminary Studies to Test the Effects of Ambulatory Voice Biofeedback: Study 2

NCT Number: 03416868

Date: August 14th, 2024

Study Protocol:

Study Two will involve 48 total patients (20 with phonotraumatic VH and 20 with non-phonotraumatic VH + potential 20% drop out rate), each handled as a single subject design to test if large changes in voicing occur during AVB (acquisition) and the days post-AVB (retention). This experimental design is best suited for the study since (1) AVB can only be effective via an individualized approach to therapy and (2) we aim to demonstrate improvement with AVB across subjects who will have different measures as biofeedback targets. To be offered participation, each patient must successfully complete approximately one week of pre-therapy ambulatory data (acquired from protocol 2011P002376) and will need to demonstrate that the average behavior of a particular vocal function measure deviates by at least 1 standard deviation from normative values.

Throughout the first voice therapy session, the VHM will be worn with the goal of establishing a significant change in a voiced feature associated with perceptually improved voicing per the SLP. The SLP will use the VHM's real-time summary feedback to assess if improved voicing is significantly different than baseline. First, the baseline threshold will be based on 85th and/or 15th percentiles of measures from baseline that were >1 standard deviation away from our normative database. Second, the improved voicing must be over 90% compliant for at least 1 feature.

During the first therapy session, once the clinician has established that the patient can modify their voicing the patient will qualify for ambulatory monitoring without AVB the following week. Of note, patients will have already been trained on VHM use without AVB in the 2011P002376 protocol and completed a week of monitoring. After the first voice therapy session, each patient will begin monitoring without AVB in daily life. There will be no feedback in the patient's daily life so that we can evaluate if the patient can improve their voicing outside the therapy session without feedback.

The patient will receive monitoring with AVB during their second voice therapy session and subsequent monitoring in daily life. Starting in the second therapy session, the SLP will review the patient's performance over the previous week. The patient will be trained on using, and begin receiving, feedback for the last half of their therapy session. The training will include presenting how the biofeedback parameter is affected by their success. The patient will be asked to produce the targeted vocal behavior using negative practice in which s/he will be asked to purposefully perform a voicing task correctly and incorrectly to experience biofeedback cueing. The AVB will be provided throughout the second half of the first therapy session so that the patient can have practical training on its use and the clinician can ensure the AVB is tracking with improved voicing appropriately. During the ambulatory voice recordings, the patient will receive feedback on all 4 days of monitoring. During the week that the patient receives feedback, starting after this second therapy session, [name] will set up the VHM to provide feedback.

Starting in the third therapy session, the SLP will review the patient's performance over the previous week. If the patient did not respond to the feedback during week 2 monitoring, the study will stop for the patient and they will be paid for two voice therapy sessions and 8 days of monitoring (4 days per week). If the patient did respond to the feedback, they will qualify to continue the study during their third therapy session and in daily life the following week. The patient will be monitored during the third therapy session and for 4 days the subsequent week without the feedback. The purpose of the third week of monitoring is to see if the patient can retain their vocal improvements without the feedback.

The schedule of ambulatory monitoring time within each therapy week will be: 20 minutes of accumulated phonation time after the therapy session (Day 1), 40 minutes of phonation time for each of the next consecutive two days (Days 2 and 3), and 40 minutes of phonation time for the day before the patient's subsequent voice therapy session (Day 4). AVB will be provided during all days only during week 2. The specific AVB used will depend upon patient preference (e.g., some patients may find the frequent vibrotactile cueing of immediate feedback to be too distracting at their job). Throughout the study, subjects may be prompted to take a picture of their neck with the smartphone to document correct placement of the accelerometer.

TABLE II. Study 2 time points and associated visits/procedures.

Treatment Week 1

MGH Voice Center

Investigator places VHM before voice therapy, voice therapy session is recorded, recording is uploaded onto Voice Center database, VHM reattached to subject, Day 1 recording begins

Daily life

Day 1 recording without feedback starts immediately after voice therapy. Wear VHM until record 20 minutes of voicing.

Day 2 and Day 3 recording without feedback will be two consecutive days post-Day1. Wear VHM until record 40 minutes of voicing

Day 4 recording without feedback will be the day before Week 2's voice therapy session. Wear VHM until record 40 minutes of voicing.

Treatment Week 2

MGH Voice Center

Investigator places VHM before voice therapy, voice therapy session is recorded. Subject will be trained to use and get biofeedback during therapy. Recording is uploaded onto Voice Center database, VHM reattached to subject, Day 1 recording begins

Daily life

Day 1 recording with feedback starts immediately after voice therapy. Wear VHM until record 20 minutes of voicing.

Day 2 and Day 3 recording with feedback will be two consecutive days post-Day 1. Wear VHM until record 40 minutes of voicing

Day 4 recording with feedback will be the day before the next voice therapy session. Wear VHM until record 40 minutes of voicing.

Treatment Week 3

MGH Voice Center

Investigator places VHM before voice therapy session 3, voice therapy session is recorded, recording is uploaded onto Voice Center database, VHM reattached to subject, Day 1 recording begins

Daily life

Day 1 recording without feedback starts immediately after voice therapy. Wear VHM until record 20 minutes of voicing.

Day 2 and Day 3 recording without feedback will be two consecutive days post-Day1. Wear VHM until record 40 minutes of voicing

Day 4 recording without feedback will be the day before Week 2's voice therapy session. Wear VHM until record 40 minutes of voicing.

Statistical Analysis Plan:

Study Two will use one repeated measure ANOVA with 3 levels (pre-therapy days, AVB days pooled together (therapy week 2), retention days pooled together (after stopping AVB, therapy week 3) for the outcome variable of overall percentage compliance. The finding of interest is the main effect of "Level." Appropriate post hoc tests will be conducted on the main effects (if significance is achieved). It is hypothesized that the ANOVA will show, compared to pre-therapy, a significantly increased percentage compliance for all other levels. This result will demonstrate the expected large AVB effect that fades after AVB removal (smaller improvements during retention days than AVB days).

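### Does enrolling 48 patients fall short of the 20 + 20 target once the 20% drop-out allowance is applied?

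*Combined protocol and SAP*

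**What the plan says.** The only sample size statement is the opening sentence of the Study Protocol section: "48 total patients (20 with phonotraumatic VH and 20 with non-phonotraumatic VH + potential 20% drop out rate", with the bracket closing there. It gives a total, two group sizes and an allowance joined by a plus sign. It does not say whether the 20% is a share of the 40 or of the 48, and it does not say how the 48 divide between the two groups. No significance level, power, effect size or required number of completers is given anywhere in the document.

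Three other places bear on how many patients reach the analysis:

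- On the first therapy session, the Study Protocol section says that "once the clinician has established that the patient can modify their voicing the patient will qualify for ambulatory monitoring without AVB the following week".
- On the third session, it says: "If the patient did not respond to the feedback during week 2 monitoring, the study will stop for the patient".
- The Statistical Analysis Plan section specifies "one repeated measure ANOVA with 3 levels (pre-therapy days, AVB days pooled together (therapy week 2), retention days pooled together", the last level being the week after feedback is withdrawn. Diagnosis group is not a factor in that model.

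**The concern.** Adding the drop-out percentage to the target, instead of dividing the target by the retained fraction, is a familiar slip in sample size sections. A drop-out rate is ordinarily a proportion of the patients who entered, since only they can leave. Read that way, 48 enrolled patients with a 20% loss do not yield 20 + 20, and the total would have to be 50. The 8 extra patients cover a loss of only 16.7% of those enrolled.

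If 40 were the number needed for a stated power, the study would be slightly undersized on its own assumption. The worry grows if patients stopped for non-response after week 2 have to come out of the same allowance, because they have no week 3 data for the third level of the ANOVA.

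**Working it through.** **Inputs, all from the opening sentence of the Study Protocol section.** Target: "20 with phonotraumatic VH and 20 with non-phonotraumatic VH", so 20 + 20 = 40. Allowance: "potential 20% drop out rate", base not stated. Total: 48.

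**Reproducing the plan's figure.** Target × (1 + rate) = 40 × 1.20 = 48. This matches exactly, with no rounding.

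**Size of the allowance.** 48 − 40 = 8 patients. As a share of the target, 8/40 = 20.0%. As a share of those enrolled, 8/48 = 16.7%.

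**Reading A: the 20% is a share of the 40.** 48 − 8 = 40 remain. There is no shortfall.

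**Reading B: the 20% is a share of those enrolled.**

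- Remaining: 48 × (1 − 0.20) = 38.4, which is 40 − 38.4 = 1.6 below target.
- Per group, assuming a 24:24 split (not stated): 24 × 0.80 = 19.2, which is 20 − 19.2 = 0.8 below 20.
- Enrolment needed to keep 40: 40/(1 − 0.20) = 50, two more than planned.
- Effect on precision: the standard error of a mean scales with 1/√n, so the ratio is √(40/38.4) = 1.021, about 2% larger.

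**Which reading fits the text.** Reading A returns the sponsor's total exactly; Reading B returns 50. The plus sign in the sentence also describes an addition to the two groups.

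**What depends on the difference.** No power is stated, so none is lost. The ANOVA has no group term, so moving from 20 to 19.2 per group changes no planned comparison.

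**Other losses.** The stop for week 2 non-responders does remove patients from week 3. The documents give no expected non-response rate and do not say whether these patients fall within the 20%, so their number cannot be computed. The session 1 sentence says when a patient qualifies for monitoring. It does not say that a patient who has not yet qualified leaves the study, or that such a patient counts among the 48, so it should not be counted as a second planned exit.

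**The case for a change.** The strongest case for a change has three parts.

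First, the ordinary meaning of a drop-out rate is a share of those enrolled, and on that meaning 48 does not deliver 40. This is a fair account of common usage. But it is brought in from outside the document, and it fits the stated total less well than the additive reading does. The word used is also potential: the 20% is a contingency, not a forecast that 38 patients will finish.

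Second, this is the only sample size statement and nothing else supports it, so its base ought to be unambiguous. It is true that the base is not stated. Yet the absence of a power calculation works the other way on consequences: with nothing resting on exactly 40, a difference of 1.6 patients alters no claim in the plan. Saying which base was meant would be a courtesy to the reader and would leave enrolment, procedures and analysis as they are.

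Third, week 3 is open only to patients who responded in week 2, while the ANOVA compares pre-therapy, week 2 and week 3. That stands as a real question, but it concerns selection and missing data. It would be the same question with 48 or 50 enrolled and with either base for the 20%, so it gives no support to the arithmetic point.

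**Conclusion.** No change to the plan follows. The total of 48 is 40 plus 20% of 40 and agrees with its own wording. What is missing is the base of a percentage, a gap that any reader can close by reproducing the total.

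If the 20% were a share of those enrolled, the shortfall would be 1.6 patients overall (0.8 per group on an assumed 24:24 split), with a standard error about 2% larger. That would affect no stated power and no planned comparison.

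The conclusion rests on two things: the additive reading, which is the one that reproduces 48, and the fact that the document ties 40 to no power, precision or minimum number of completers. It does not cover the effect of stopping non-responders after week 2, which is a different issue and cannot be sized from the documents.

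### One pre-therapy week selects the patient, sets the compliance threshold and serves as the ANOVA reference, so the contrast with pre-therapy is not centred on zero when voicing is unchanged

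*Combined protocol and SAP*

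**What the plan says.** The combined document uses the pre-therapy recording three times.

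- **Selection** (Study Protocol, opening paragraph): "each patient must successfully complete approximately one week of pre-therapy ambulatory data (acquired from protocol 2011P002376"), and the average of some measure in it "deviates by at least 1 standard deviation from normative values".
- **Threshold** (Study Protocol, first therapy session): "the baseline threshold will be based on 85th and/or 15th percentiles of measures from baseline", restricted to measures more than 1 SD from the normative database. The patient must also show in the session that "the improved voicing must be over 90% compliant for at least 1 feature".
- **Comparator** (Statistical Analysis Plan): one repeated-measures ANOVA with "3 levels (pre-therapy days, AVB days pooled together (therapy week 2), retention days pooled together", "for the outcome variable of overall percentage compliance". The hypothesis is, "compared to pre-therapy, a significantly increased percentage compliance for all other levels".

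No other pre-therapy ambulatory recording is described. No pre-therapy days are held back for the comparison, and there is no adjustment for regression to the mean and no concurrent control. Treatment Week 1 in Table II (therapy, four monitored days, no feedback) is recorded but is not an ANOVA level.

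**The concern.** A percentile of a week, applied back to that same week, returns the percentile. Pre-therapy compliance would therefore be close to 15% or 85% in every patient, depending on which side of the threshold counts as compliant. It would be a product of the rule rather than a measurement. Later weeks differ in two ways: they were not chosen for being extreme, and the threshold was not fitted to them. The pre-therapy contrast thus compares a pinned constant with a quantity that drifts even when the patient's voicing stays the same.

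This ANOVA is the only inferential analysis in the plan, and its hypothesis is worded as a rise from pre-therapy. The plan sets no minimum change, so a shift of a few points could be enough for a significant result. In the opposite direction, it could hide part of a real gain.

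**Working it through.** **Inputs from the documents.** Evaluable patients: 20 + 20 = 40. Total: 40 × 1.20 = 48, which reproduces the stated number. Selection cut-off: 1 normative SD. Percentiles: 15th and 85th. Alpha, effect size, expected compliance and week-to-week reliability are not stated.

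**Assumptions.** Higher values are worse. A patient's weekly average is a stable level plus a weekly deviation e, with total variance 1 (normative SD units), so Var(e) = 1 - ICC. Values within a week have SD ω. Patient levels have mean μ. Voicing does not change.

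**Model.** The patient enters if the pre-therapy average is at least 1. The threshold is the p-quantile of that week, so pre-therapy compliance equals p. In a later week w,

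compliance = Φ(z_p + (e₀ - e_w)/ω), with z = -1.036 for p = 15% and +1.036 for p = 85%.

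**By hand, ICC 0.8, ω = 1.**

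1. Threshold fitting alone, without selection: Φ(z_p/√(1 + 2(1 - ICC)/ω²)) = Φ(∓1.036/√1.4) = Φ(∓0.876), giving 19.1% or 80.9%. It pulls compliance towards 50%: up from 15%, down from 85%.
2. Selection at μ = 0.5: mean e₀ among those selected = (1 - ICC)·φ(0.5)/[1 - Φ(0.5)] = 0.2 × 0.3521/0.3085 = 0.228. The selected weekly average has variance 1 + 0.5 × 1.141 - 1.141² = 0.269, so Var(e₀) = 0.16 + 0.04 × 0.269 = 0.171. Regression raises compliance on either reading.
3. Together (e₀ taken as roughly normal): Φ((z_p + 0.228)/√(1 + 0.171 + 0.2)). For 15%: Φ(-0.808/1.171) = 24.5%. For 85%: Φ(1.264/1.171) = 86.0%.
4. At μ = 1: shift 0.2 × 0.3989/0.5 = 0.160; selected variance 1 - 0.798² = 0.363; Var(e₀) = 0.16 + 0.04 × 0.363 = 0.175. For 15%: Φ(-0.876/1.172) = 22.7%. For 85%: Φ(1.196/1.172) = 84.6%, now slightly below 85%.

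The two forces add on the 15% reading and oppose each other on the 85% reading. That is why the direction is settled on one reading and not on the other.

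**Simulation of the planned three-level ANOVA.** No true change, n = 40, μ = 0.5, assumed two-sided alpha 0.05, 2,000 trials per cell. Each cell shows expected Week 2 compliance, then the ANOVA rejection rate.

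| ICC | 15%, ω = 1 | 15%, ω = 2 | 85%, ω = 1 | 85%, ω = 2 |
|---|---|---|---|---|
| 0.95 | 17.6%; 51% | 16.0%; 34% | 85.1%; 5% | 85.3%; 10% |
| 0.90 | 20.0%; 81% | 16.9%; 62% | 85.5%; 6% | 85.7%; 17% |
| 0.80 | 24.5%; 98% | 18.9%; 91% | 86.1%; 10% | 86.5%; 30% |
| 0.70 | 28.7%; 100% | 20.8%; 98% | 86.7%; 16% | 87.1%; 45% |

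With almost perfect week-to-week stability (ICC 0.9999) the 15% reading gives 15.0% and 5% rejection, so the artefact needs week-to-week variation.

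**Wider range.** ICC 0.7 to 0.9, ω 1 to 2, μ 0 to 2.5, paired test in the favourable direction at nominal 2.5%, not conditional on the ANOVA:

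| Contrast | Spurious change (points) | Rejection |
|---|---|---|
| AVB week vs pre-therapy, pinned at 15% | about +0.7 to +17 | about 11% to 100% |
| AVB week vs pre-therapy, pinned at 85% | about +3.7 to -4.8 | about 0% to 81% |
| AVB week vs Week 1 | about 0 | about 1% to 4% |

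On the 85% reading the gain is positive at low patient means and negative at high ones.

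**The case against.** **The outcome is not defined.** The SAP does not say that overall percentage compliance is scored against the first-session threshold, or that the baseline week and the pre-therapy days are the same data. The threshold wording is loose, and a two-sided or multi-feature rule would give neither 15% nor 85%. This stands, and the point is conditional on it. But no other threshold and no other pre-therapy recording is described, so this is the natural reading.

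**The bias may be nil.** These are voice patients, whose mean may lie well above 1 SD. With pre-therapy compliance pinned at 85%, ω = 2 and a mean of 1.5 SD, the bias is -0.01 to +0.13 points and false positives are 3% to 5%. Beyond that it turns negative. This also stands. A reader might infer that the design always flatters AVB; the documents do not support that, because they leave open which side of the threshold is compliant and give no patient mean or reliability.

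**Post hoc tests follow only a significant main effect.** That gate lowers the rates but does not remove the problem. With mean 0 to 1 and ω = 2, the 85% range falls from 8–82% to 4–77%, and the low end on the 15% reading falls from 39% to 31%.

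**The study looks for large changes.** A reader might infer that a positive result would be worthless. That goes too far: a gain well beyond the ranges above could not come from this artefact, and the pinned level does not itself bias the AVB-versus-retention comparison.

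**Standard errors.** A reader might also infer that the near-constant level makes the post hoc standard errors wrong. The SAP asks only for appropriate post hoc tests and names no pooled error term, so that criticism does not describe the written plan.

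**Conclusion.** The point holds in conditional form. If compliance is scored against the pre-therapy percentile threshold, the planned comparison with pre-therapy is biased under no change, except where the two forces happen to cancel. Confidence in that is high. Confidence in size and direction is medium, because both rest on assumed reliability, within-week spread and patient mean, and on which side of the threshold is compliant. Pinned at 15%, the bias is upward throughout the range examined; pinned at 85%, it can go either way. It can decide significance but cannot account for a very large rise. It should be fixed before analysis; it does not invalidate the data collected.

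**What to change.** Change the Statistical Analysis Plan as follows.

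- Add Week 1 (therapy, no AVB) as a level.
- Make AVB week minus Week 1 the main inferential contrast and retention week minus Week 1 the second, each as a paired comparison.
- Score every week against the same threshold, fixed in advance, and state which side of it counts as compliant.
- Report pre-therapy compliance descriptively only.

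**Cost.** SAP wording only, since Week 1 is already recorded. The gain will look smaller, because Week 1 already contains some therapy effect.

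**What it does not solve.** Week 1 as reference does not separate AVB from continuing therapy or from the fixed order of weeks. The retention contrast covers only patients who responded in Week 2, because the Study Protocol stops the study for the others. The calculation above did not model that filter, so the main contrast should use every patient with both Week 1 and Week 2 data.

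Splitting the pre-therapy days, with one half for eligibility and threshold and the other for comparison, is a weaker alternative. Any deviation shared by the whole week stays in both halves, and the enrolment and threshold rules in the Study Protocol would have to change.

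### Week 2 non-responders have no Week 3 data, so the three-level ANOVA may analyse responders only, inflating the gains and creating or exaggerating a fade

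*Combined protocol and SAP*

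**What the plan says.** The Study Protocol makes entry to Week 3 depend on Week 2: "If the patient did not respond to the feedback during week 2 monitoring, the study will stop for the patient". Only responders go on. Response is given no measure or cut-off. The nearest description is "Starting in the third therapy session, the SLP will review the patient's performance over the previous week". Stopped patients are paid for eight monitored days, which implies that their Week 2 recordings exist. The aim of the last week is stated: "The purpose of the third week of monitoring is to see if the patient can retain their vocal improvements without the feedback".

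The Statistical Analysis Plan has one analysis, a repeated-measures ANOVA with three levels. The first two are pre-therapy and Week 2. The third is "retention days pooled together (after stopping AVB, therapy week 3) for the outcome variable of overall percentage compliance". The hypothesis is "It is hypothesized that the ANOVA will show, compared to pre-therapy, a significantly increased percentage compliance for all other levels", and the SAP adds: "This result will demonstrate the expected large AVB effect that fades after AVB removal (smaller improvements during retention days than AVB days". It names no analysis set, no treatment of a missing level and no alternative model.

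**The concern.** The stop rule and the analysis do not fit together. Non-responders lack the third level by design, and a standard repeated-measures ANOVA excludes any patient who lacks a level. Their Week 2 data are then discarded from the Week 2 versus pre-therapy comparison as well, although nothing about that comparison requires Week 3.

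If the judgement of response follows Week 2 compliance, patients are kept because they did well on one of the levels being compared. Three things can follow.

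- The Week 2 gain is too large.
- If response means a rise over pre-therapy, the Week 3 gain is too large as well, because low pre-therapy values are also selected.
- Week 2 variation that does not carry over to Week 3 disappears in Week 3, giving a fall that the SAP would read as fading.

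The last matters most when a real gain is fully retained. Both rises are then genuine, and a false fall alone completes the hypothesised pattern.

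**Working it through.** **The plan's own figure.** The Study Protocol's total is reproduced by (20 + 20) × 1.2 = 48. The 20% allowance is for drop-out and is not tied to non-response. No SD, correlation, effect size, alpha or expected share of non-responders is given, so everything below is illustration.

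**Assumed inputs.** Forty patients; normal compliance with SD 8 points at each level; equal correlation ρ = 0.6 (range 0.4 to 0.8); the same true gain in everyone, fully retained in Week 3; complete cases; response means that Week 2 minus pre-therapy exceeds a cut c.

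**Formula.** The Week 2 minus pre-therapy difference has SD 8 × √(2(1 − 0.6)) = 7.155. With z = (c − gain)/7.155, the share stopped is s = Φ(z), and

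Week 2 bias = 7.155 × φ(z)/(1 − s).

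The slope of the Week 3 gain on the Week 2 gain is 64(1 − ρ)/(2 × 64(1 − ρ)) = 1/2. So the Week 3 bias is half the Week 2 bias, and the other half appears as a false fall.

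| True gain | Response rule | z | Stopped | Week 2 bias | Week 3 bias = false fall |
|---|---|---|---|---|---|
| 0 | any rise | 0 | 50% | 7.155 × 0.399/0.500 = +5.7 | 2.9 |
| 8 | any rise | −1.118 | 13% | 7.155 × 0.2135/0.868 = +1.8 | 0.9 |
| 8 | rise above 5 | −0.419 | 34% | 7.155 × 0.365/0.662 = +3.9 | 2.0 |
| 16 | any rise | −2.236 | 1% | 7.155 × 0.0327/0.987 = +0.2 | 0.1 |
| 16 | rise above 5 | −1.537 | 6% | 7.155 × 0.122/0.938 = +0.9 | 0.5 |

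For ρ from 0.8 to 0.4, the first row becomes +4.0 to +7.0 in Week 2 and 2.0 to 3.5 in Week 3. If 17% stop (close to all eight of the extra patients, 8/48), the biases are +2.2 and +1.1 whatever the true gain.

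**Simulated error rates** (ρ = 0.6, complete cases, unadjusted two-sided paired t-tests at 5%):

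- No effect, any rise: the Level test rejects in about 99% of trials, both rises are significant in about 45%, and both rises plus the fall in about 10%.
- Retained gain of 8: a false significant fall in about 11% (any rise) and 32% (rise above 5), against a nominal 2.5%. Over ρ = 0.4 to 0.8 the ranges are roughly 5% to 15% and 25% to 33%.
- Retained gain of 16: about 3% to 7%.

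**Sensitivity to the response rule.** With no effect and response judged against Week 1, the biases are Week 2 +2.8 and Week 3 0.0. Against a fixed cut they are +2.6 and 0.0. The full pattern then appears in 0.2% of trials. If pre-therapy compliance is nearly constant, the any-rise rule with no effect gives Week 2 8 × 0.798 = +6.4, Week 3 0.6 × 6.4 = +3.8 and a fall of 2.6.

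**Check that selection is the cause.** In a separate simulation in SD units (48 enrolled, correlation 0.3 to 0.7, lowest 20% of Week 2 gains stopped, no effect), the Level test rejected in 57% to 60% of trials, against about 5% with everyone kept. Losing 20% independently of compliance gave no bias. When individual response was fully persistent and noise-free, the Week 2 gain rose from 0.80 to 1.08 SD but no fade was created.

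**The case against.** The strongest reply is that the mechanism needs conditions the documents do not state. The SAP does not say complete-case, and response is not tied to compliance. A created fade also needs week-to-week variation; with fully persistent response there is none. This stands as a limit, and the point is conditional for that reason. It does not supply the missing analysis set.

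The plan also expects a large effect. At a gain of 16 points the Week 2 bias is under 1 point at ρ = 0.6. That stands too, but a plan should not rely on the result it sets out to test.

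The error rates above use unadjusted tests, whereas the SAP runs unspecified post hoc tests only after a significant Level effect. With that gate and a Bonferroni correction (assumed), the false fall at a gain of 8 drops to about 5% and 17%, and the full pattern under no effect to about 2%. The adjusted nominal rate for a fall is 0.05/3/2 = 0.8%, so the excess shrinks but remains. The SAP also does not say that the fade itself must be significant; a smaller observed gain in Week 3 could be read as fading without any test.

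Finally, asking about retention only in patients who improved fits the stated purpose of Week 3. That is accepted. It does not justify removing non-responders from the Week 2 comparison.

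**Conclusion.** The concern holds in its conditional form and should be fixed. What follows from the documents alone is that Week 3 is missing by design for non-responders, the only analysis needs Week 3, and nothing says who is analysed. If the ANOVA is run on complete cases and response tracks Week 2 compliance, the Week 2 gain is inflated. The Week 3 gain is inflated too if response is judged as a rise over pre-therapy, and a fall between the two weeks is created or exaggerated when part of the Week 2 variation is not shared with Week 3. The size depends on the response rule, the share stopped and the correlation, none of which the documents give. It could range from negligible (large effect, few stopped) to several percentage points (weak effect, many stopped).

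**What to change.** Leave the stop rule as it is and change the SAP.

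1. Test Week 2 against pre-therapy in every patient with Week 2 recordings, whatever their response. In simulation this contrast had bias of about 0 and rejected in about 5% of trials with no effect. State that it includes the effect of the therapy sessions. Show Week 2 against Week 1 (after therapy, no biofeedback) beside it, noting that it still includes the second session.
2. State how response was judged and how many patients stopped. Report Week 3 in responders as conditional on Week 2 response, and do not read their fall from Week 2 as fading without noting regression to the mean.
3. As support only, fit a likelihood-based mixed model to all available data. State that its overall Week 3 mean is an extrapolation that relies on response having been judged from the recorded data and on the model form.

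This costs wording only: no extra patients, visits or recordings. The biofeedback estimate will be smaller than the responder-only figure. The mixed model's Week 3 estimate can be imprecise. In the illustration its SD is 1.3 to 1.7 points at a gain of 8, against 1.1 with full data. With no effect it is 2.6 under the any-rise rule and about 9 (8.6 and 9.6 in two runs) under the 5-point rule.
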